Our primary outcomes were egg intake, protein intake (total), protein intake from animal-based foods and adverse events. Secondary outcomes were lean body mass and various functional measures of lean body mass. Variables of potential influence on these outcomes were also assessed, to include various demographic and lifestyle characteristics, energy intake, BMI, usual physical activity levels, health-related quality of life, reasons for eating / not eating eggs, and recipe feedback (intervention group only) Morton et al., 2017). Some of these additional variables were included in analyses to control for potential confounding, some were used only to describe the sample and some were used to investigate further any reasons for intervention success or failure.

Primary Outcomes:

Egg intake: Egg intake was measured using two measures: an egg consumption Food Frequency Questionnaire (FFQ) measure [ref] and the egg section of a validated FFQ [SCG-FFQ, Clark, 2017; Masson et al., 2003]. The egg consumption FFQ requested frequency of consumption of 18 preparations of egg: boiled eggs (hot), hard boiled eggs (cold), fried eggs, scrambled eggs, poached eggs, omelettes, scotch eggs, quiches/savoury flans, egg sandwiches, egg salad, custards, meringues, sweet flan/crème caramel, duck/quail's eggs, raw eggs, egg yolk separate from the white, and egg white separate from the yolk. For each type of egg, participants were asked to complete number of measures (e.g. 1 egg, 1 slice) consumed per day (1, 2, 3, 4, 5+) on number of days per week, using response options 1 - 7 days per week, once or twice per month, or rarely / never. Responses were converted to number of eggs eaten per month, where the category 'rarely or never' was counted as 0 times eaten per month, 'once or twice per month' as 1.5 times, and 1 to 7 days per week, as 4, 8, 12, 16, 20, 24, and 28 times per month, respectively. All foods were considered to contribute equal portions of eggs, excepting the egg dishes custards, meringues, and sweet flan / crème caramel, where each consumption was considered as 0.5 portions, because a standard portion tends to be less than one egg.

The SCG-FFQ is a validated FFQ, developed by the Scottish collaborative group, measuring dietary intake over the last two-three months (Clark, 2017; Masson et al., 2003). The section on egg intake consists of

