three questions: number of measures (eggs) per day, and the number of days per week they eat 'Boiled or poached eggs'; 'Fried eggs'; and 'Scrambled eggs or omelette'. Response options were used and converted to monthly egg intake as above.

Protein intake: Protein intake was measured using the complete SCG-FFQ, where food intake data were converted to protein intake and protein intake from animal sources, by the Scottish collaborative group (Clark, 2017). Protein intake from animal sources consisted of protein intake from meat, fish, eggs, and dairy foods. Protein intake is known to be related to egg intake (Ruxton, Derbyshire, & Gibson, 2010, questionnaire study), to muscle mass, strength and function (Houston et al., 2008; Loenneke, Loprinzi, Murphy, & Phillips, 2016; Tieland et al., 2012), and to positive health outcomes in older adults (Hannan et al., 2000; Lord, Chaput, Aubertin-Leheudre, Labonté, & Dionne, 2007). Animal based proteins contain all essential amino acids and are considered high quality protein sources (van Vliet, Burd, & van Loon, 2015). Animal protein stimulates a higher net protein synthesis than a high plant protein diet (Pannemans, Wagenmakers, Westerterp, Schaafsma, & Halliday, 1998). These measures also allowed investigation of any replacement of other high protein foods by egg based protein foods.

Adverse events: To assess adverse events, participants were asked whether during the previous month they had experienced any of the following effects more or less often than usual: nausea, digestive issues (e.g. constipation or diarrhoea), stomach aches/cramps, hunger, bloating/uncomfortable fullness, thirst, headaches, fatigue/tiredness, restlessness, dizziness, or skin rashes. If they answered yes to any of these questions, they were asked if they knew of any reason for this, or they had experienced anything else that was different than usual.

Secondary Outcomes:

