Functional measures of lean body mass: Physical performance was assessed using a short physical performance battery (SPPB) (Guralnik et al., 1994), consisting of three physical functioning tests measuring: lower body strength (chair stands), standing balance, and walking speed (8-foot walk). For the chair stands, participants were asked to stand up from a chair and sit down five times with their arms across the chest and time is measured. For the balance test, participants were instructed to stand in different positions: side-by-side, semi-tandem, and full-tandem position, while being timed for 10 seconds, or until they lost their balance. Walking was measured by asking the participant to walk an 8-foot walking course, at their usual speed, as if they were walking down the street to go to the shops. Times were recorded twice, and the fastest used for analyses. Scores from zero to four are derived for each of the three components and totalled following the instructions by Guralnik et al. (Guralnik et al., 1994). Total SPPB scores range from 0 to 12 with a higher score indicating better physical performance. The measures are relatively quick, include activities that are used in everyday life, and are non-invasive for the participants. SPPB measures have been linked to self-reported disability, predict mortality and nursing home admission (Guralnik et al., 1994), and have been recommended for measuring physical performance in frail old people (Cruz-Jentoft et al., 2010). Statistically significant improvements in SPPB scores have been found in older adults following increased protein intake (Tieland et al., 2012) and the method can measure clinically meaningful changes (Kwon et al., 2009).

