Usual Physical Activity: Physical activity, as energy expended in physical activity per week, was assessed using the Community Healthy Activities Model Program for Seniors (CHAMPS), a physical activity questionnaire for older adults (Stewart et al., 2001). The CHAMPS lists a variety of light, moderate and vigorous physical activities, and requests weekly frequency of performing each activity in number of hours per week (response options: less than 1 hour, 1-2.5 hours, 3-4.5 hours, 5-6.5 hours, 7-8.5 hours, and 9 or more hours). Responses were converted to four outcomes (Stewart et al., 2001), and estimated caloric expenditure per week on all activities was used for analyses. Physical activity is strongly related to muscle mass and strength (Cruz-Jentoft et al., 2010; Goodpaster et al., 2008), and a recent review showed that experience in exercise made protein supplementation with resistance training more effective (Morton et al., 2017). Studies also show associations between higher egg intake and low physical activity (Hu et al., 1999).

Health related quality of life: Health related quality of life (HR QoL) was assessed using the short form-36 questionnaire (SF-36) (Ware Jr & Sherbourne, 1992). Scores for all nine domains were generated (Ware Jr & Sherbourne, 1992) and added up to give a total SF-36 score, where a higher score suggests a greater HR QoL. SF-36 scores have been associated with muscle strength and physical performance (Syddall, Martin, Harwood, Cooper, & Sayer, 2009).

Reasons for eating or not eating eggs: Reasons for eating / not eating eggs were assessed by questionnaire, as previously developed [ref], to give insights into other possible barriers to trying the recipes.

Recipe feedback: Intervention group participants also received a recipe feedback form in the post after the 12 week intervention and after the following 12 weeks. This form asked for comments on which recipes and herb/spice packets they used or did not use, and why. Recipe feedback forms were sent by post after the test sessions, so that the completion of these does not impact on our primary outcomes, by a researcher unassociated with testing to maintain blinding.

Procedure

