Ethical approval for this study was granted by the Research Ethics Committee of Bournemouth University, prior to commencement. Participant recruitment started in May 2016, and test sessions were run from June 2016 to April 2017. The study was registered at ClinicalTrials.gov in May 2016 (NCT02777918).

Data analyses

Data were analysed using IBM SPSS Statistics for Windows, version 22, using an Intention-to-treat approach. First, all measures were tested for normality. All baseline measures were then compared

between the intervention and control group using χ^2 tests and Mann-Whitney U tests. Demographic and lifestyle characteristics were used to describe the sample. Correlations were investigated between all baseline measures. Multiple linear regression analyses were then used for the main analyses (Vickers & Altman, 2001). The effect of the intervention on all outcome measures was assessed using multiple linear regression, controlling for age, gender, baseline measures of the dependent variable, previous participation in related studies, and measures of total protein intake, BMI, usual physical activity and HR QoL score as assessed at the same time. Previous participation was included in regression models to allow for possible demand characteristics. Energy intake was not included in regression models following high correlations with BMI. Other demographic and lifestyle characteristics were also not included to maintain statistical power (Howell, 2012]. Separate regression models were used to predict egg intake, total protein intake, protein intake from animal sources, adverse events, lean body mass, physical performance, handgrip strength, and leg extensions as the dependent variables. Similar analyses were conducted once at the end of the 12 week intervention (T2) and once at the end of the following 12 weeks (T3). Egg intakes from the two different measures were compared using correlations and multiple linear regressions were conducted for both measures. Reasons for eating / not eating eggs and details on recipe feedback will be analysed further at a later date. These data and some of the data of participant demographic and lifestyle characteristics will be published elsewhere in exploratory analyses investigating intervention success / failure. Missing data were completed using last observation carried forward. Data are reported using means and standard deviations.

Figure 1: Schematic overview of the study design

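### Does the unstated coding of the adverse-event outcome mean that improvements are counted as harms?

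*Combined protocol and SAP*

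**What the plan says.** The Outcomes section sets the status of the measure: "Our primary outcomes were egg intake, protein intake (total), protein intake from animal-based foods and adverse events". Under Primary Outcomes, the adverse-events paragraph says that "participants were asked whether during the previous month they had experienced any of the following effects more or less often than usual", and lists 11 effects, from nausea to skin rashes, with hunger and thirst among them. It continues: "If they answered yes to any of these questions, they were asked if they knew of any reason for this". The same follow-up also covered any other departure from the participant's normal state. That is all the plan says about the instrument.

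Data analyses then states: "Separate regression models were used to predict egg intake, total protein intake, protein intake from animal sources, adverse events" and the remaining outcomes. The models are multiple linear regressions, run once at T2 and once at T3. They adjust for the baseline value of the same variable, among other covariates. A regression of this kind needs one number per person at each session. The plan does not say whether that number is a count, a yes/no indicator or a net score, nor which direction of change is adverse.

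Several other measures are described more fully. For egg intake, "Responses were converted to number of eggs eaten per month", with each response category given a value. For physical performance, "Total SPPB scores range from 0 to 12 with a higher score indicating better physical performance". For quality of life, the domain scores are "added up to give a total SF-36 score, where a higher score suggests a greater HR QoL".

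**The concern.** The question covers change in both directions, and the only answer mentioned is a yes. Read literally, a participant whose constipation eased gives the same answer as one whose constipation began. If those answers were summed, the outcome labelled adverse events would measure symptom change of any kind.

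The stakes would be real. A diet with more eggs and protein could plausibly shift hunger, fullness or digestion either way, so improvements need not balance between the groups. An intervention that reduced hunger could appear to cause harm, and one that caused harm while also suppressing improvements could appear neutral. Even with improvements balanced, counting them would add noise to the comparison. The contrast with the scoring rules for egg intake, SPPB and SF-36 makes the silence on a primary outcome stand out.

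**Working it through.** **The plan's own figure.** The only design calculation concerns total protein intake. The inputs, from the Sample size section, are a difference of 12.7 g, an SD of 20.3 g, alpha 5% (two-sided) and power 0.8. Then n = 2 × (1.960 + 0.842)² × 20.3² / 12.7² = 15.70 × 2.555 = 40.1, rounded up to 41 per group. It reproduces, but it has no bearing on adverse events. The document gives no symptom rate, so every rate below is an assumption.

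**What the feared scoring would do.** Let h be the group difference in worsened symptoms per person and b the difference in improved symptoms.

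- Scoring any change estimates h + b.
- Scoring worsening estimates h.
- The gap is b, which is zero if improvements are balanced.

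Assumed cases:

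| h | b | any change | worsening only |
|---|---|---|---|
| 0 | 0.20 | 0.20 | 0 |
| 0.20 | 0 | 0.20 | 0.20 |
| 0.20 | −0.20 | 0 | 0.20 |

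The same holds for a single item. Suppose 10% of controls report it more often and 10% less often, so 20% report a change. An intervention group at 10% and 20% gives 30% against 20%, an excess with no extra worsening. An intervention group at 20% and 0% gives 20% against 20%, which hides a doubling of worsening.

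**Noise when b = 0.** For independent Poisson counts with w worsened and i improved symptoms per person, the standard error of the difference is √(2w/n) for worsening and √(2(w + i)/n) for any change. The ratio is √(1 + i/w), which is 1.22, 1.41 or 1.73 for i/w of 0.5, 1 or 2. With w = 0.5:

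- n = 50: the half-width is 1.96 × √(1/50) = 0.277 for worsening, and 0.339, 0.392 or 0.480 for any change.
- n = 41: the half-width is 1.96 × √(1/41) = 0.306 for worsening, and 0.375, 0.433 or 0.530 for any change.

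Shifts of 0.05 to 0.20 are therefore smaller than the trial's own uncertainty under these assumptions. That does not excuse a bias, but it puts the illustrations in proportion.

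**Limits of this arithmetic.** It describes an unadjusted comparison. The planned models also adjust for total protein intake, BMI, physical activity and quality of life measured at the same session. These are post-randomisation variables, so the planned coefficient is in general neither h nor h + b. The half-widths also ignore that couples were allocated together.

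**Does the text show that any change was scored?** Three readings fit the adverse-events paragraph equally well:

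1. The form had separate options for more often and less often, and the prose condenses them.
2. The form had one yes/no box per effect, and the follow-up answers reveal direction.
3. The form had one yes/no box, and direction is lost.

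Only under the third is the mixing unavoidable. The plan's wording does not select it, and Data analyses names the variable only by its label.

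**The case for a change.** The strongest case for acting is that this is a primary outcome, and the only one concerned with harm, which a reader could not reproduce from the text. That h + b differs from h is algebra and needs no assumed rate, and b = 0 cannot be presumed for a dietary intervention. The omission is not an effect of redaction or extraction, since the paragraph reads as complete. A sentence would settle it cheaply.

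Much of this stands. The scoring rule is missing, and a report of the trial should say which answers were counted, in which direction, and how the items were combined. The comparison with other measures is less telling than it looks: the food neophobia and sarcopenia-symptom questionnaires also have no scoring stated, and the protein conversion is left to the group that supplied the food questionnaire. The text simply varies in detail.

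What does not stand is the step from a missing rule to a wrong one. No sentence commits the analysis to counting improvements, and the outcome's name points the other way. The obvious recoding has weaknesses of its own. Counting worsening while dropping hunger would redefine a listed primary outcome after data collection. It would also keep thirst, whose direction is no clearer. Inferring direction from the stated reasons could reveal allocation if those answers mention eggs or recipes.

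**Conclusion.** The plan leaves a detail unstated; it does not state a rule that gives a wrong result. Analysts with the questionnaire in hand would fill the gap sensibly by treating a symptom reported more often as the adverse event, coded the same way at all three sessions. For hunger and thirst, where neither direction is plainly a harm, they would report both. The same form was used at T1, T2 and T3, and testing ended in April 2017, so nothing in the conduct of the trial could be altered in any case.

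The size of the problem is zero if worsening was counted and b symptoms per person in an unadjusted comparison if any change was counted. No value of b can be drawn from the document, so the tabulated shifts illustrate the mechanism and are not evidence about this trial.

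The conclusion rests on direction having been recorded or being readable from the answers. If it turned out not to be, the result could be described only as symptom change and would not support a statement about harm. That concerns how the finding is worded, and the planned analysis need not change.

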Leg strength was measured in a seated position by counting number of times participants could extend their leg wearing ankle weights (of 5kg, 2.5kg, or no weights) during a set amount of time (one minute or 30 seconds). Ankle weight and time was chosen by the researcher during the first test session based on estimated ability of the participant after the participants had performed the other exercises, and held constant for all other test sessions. The 2.5kg weights and one minute duration were chosen for most participants. Handgrip strength was also measured using a hand grip dynamometer (Takei, GRIP-D, T.K.K. 5401) (Watanabe et al., 2005). Participants were asked to take three measures of handgrip strength for each hand, alternating between right and left hands, while standing up (or sitting if standing was not possible). The maximum of the six measures was reported (Roberts et al., 2011). Handgrip strength and leg extension are commonly used non-invasive measures to assess muscle function in older adults (Beasley, Shikany, & Thomson, 2013), and only take a few minutes. These measures have been associated with health related quality of life (Sayer et al., 2006), nutritional status (Norman, Stobäus, Gonzalez, Schulzke, & Pirlich, 2011), and future physical performance and disability (Rantanen et al., 1999). Handgrip strength also relates strongly to lower extremity muscle power and mobility (Lauretani et al., 2003), and has been recommended for a quick and inexpensive sarcopenia screening tool (Lauretani et al., 2003). Sarcopenia cut off points per gender based on measured handgrip strength were used to estimate sarcopenia prevalence (Cruz-Jentoft et al., 2010; Lauretani et al., 2003; Murphy et al., 2017).

Additional Outcomes:

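### Leg-extension counts from up to six load-by-duration settings are modelled as one outcome without the setting as a covariate: a mixed-unit effect and a small possible loss of precision, but no expected bias

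*Combined protocol and SAP*

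**What the plan says.** Under Secondary Outcomes (Functional measures of lean body mass), leg strength is measured by "counting number of times participants could extend their leg", with the participant "wearing ankle weights (of 5kg, 2.5kg, or no weights) during a set amount of time (one minute or 30 seconds". On who sets the test: "Ankle weight and time was chosen by the researcher during the first test session based on estimated ability of the participant". The setting is then "held constant for all other test sessions". On its distribution the plan says only: "The 2.5kg weights and one minute duration were chosen for most participants".

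The Data analyses section fits separate linear regressions with "lean body mass, physical performance, handgrip strength, and leg extensions as the dependent variables", at T2 and again at T3. Each is described as "controlling for age, gender, baseline measures of the dependent variable, previous participation in related studies", together with total protein intake, BMI, physical activity and quality of life measured at the same visit. Load and duration are not in that list. No conversion to a rate, standardisation within setting, stratification or restriction to the common setting is described for this outcome. Elsewhere the plan does spell out its conversions, for example egg dishes to monthly portions and SPPB components to 0–4 scores. Reading the leg outcome as a raw count is therefore an inference from silence, but the natural one.

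**The concern.** A count over 30 seconds and a count over 60 seconds are different quantities, and so are counts with 5 kg and with no weight. Pooling them has two consequences.

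- **Interpretation.** If the benefit is roughly proportional, the same relative gain adds more repetitions at a setting with high counts than at one with low counts. The treatment coefficient then averages over tests, and its size depends on how many people were on each. Baseline means and SDs, which have no covariate to absorb the setting, are on the same mixed scale.
- **Precision.** One slope on the baseline count has to serve both for differences between settings and for differences between people on the same setting. If those two slopes differ, some setting variation stays in the residual and widens the confidence interval.

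**Working it through.** **The plan's own figures.** The documents give no mean, SD, correlation, effect size or sample size for leg extensions. The one computed figure, in the Sample size section, is for protein intake: 2 × (1.960 + 0.842)² × (20.3/12.7)² = 40.1, rounded up to 41 per group (41.1 with the t distribution). It reproduces, but has no bearing on this outcome.

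**Number of settings.** 3 loads × 2 durations = 6 at most, hence at most 6 − 1 = 5 indicator terms.

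**Simulation inputs (all assumed).** 100 participants randomised 1:1, 3,000 runs per scenario, four settings. The majority setting has a mean of 40 counts. The other three share the remaining participants equally, with means of 20, 30, 20 (set A) or 50, 30, 20 (set B). The majority share is 60%, 75% or 90%; the plan says only that most participants had one setting. The coefficient of variation is 25%, the true gain is 10% of the setting mean, and the baseline-to-follow-up correlation r is 0.5, 0.7 or 0.9.

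For person *i* at a setting with mean *m*, treatment *t* (0 or 1), and independent standard normals *u* and *e*:

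- baseline = m(1 + 0.25u)
- follow-up = m(1 + 0.25[ru + √(1−r²)e] + 0.10t)

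**What the pooled coefficient measures.** It should be close to 10% of the average setting mean.

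- 60% majority, set A: 0.6 × 40 + (0.4/3) × (20 + 30 + 20) = 33.3, giving 3.33 counts. Simulated: 3.30 to 3.35.
- 90% majority, set B: 0.9 × 40 + (0.1/3) × (50 + 30 + 20) = 39.3, giving 3.93 counts. Simulated: 3.94 to 3.95.

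So the same 10% gain appears as about 3.3 to 4.0 counts, depending only on the mix. Within a setting it is 4 counts where the mean is 40 and 2 where it is 20. Setting indicators do not change this: the adjusted coefficients run from 3.33 to 3.97. Only an analysis within one setting, or on a rescaled outcome, gives a fixed unit.

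**Precision.** Standard error of the treatment effect with baseline count only, divided by that with setting indicators added (set A / set B):

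| Share on majority setting | r = 0.5 | r = 0.7 | r = 0.9 |
|---|---|---|---|
| 60% | 1.075 / 1.067 | 1.037 / 1.035 | 1.009 / 1.008 |
| 75% | 1.056 / 1.047 | 1.025 / 1.022 | 1.001 / 1.001 |
| 90% | 1.020 / 1.014 | 1.003 / 1.002 | 0.990 / 0.992 |

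In variance terms the worst corner is 1.075² = 1.16, and the middle of the table is 1.025² = 1.05. The largest power difference is 58.0% − 51.2% = 6.8 points (60% majority, r = 0.5, set A). At r = 0.9 the two models agree to within 0.2 points.

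**Validity.** With no true effect, the baseline-only model rejected in 5.7% of runs (75% majority, set A) and 4.5% (60% majority, set B), against 5.8% and 4.8% with setting indicators. There is no sign of type I error inflation.

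**The case against.** The strongest reply is that the design already deals with most of this. Each person is tested at the same setting at every visit, so individual change is like for like. The baseline count at that setting is in the model and absorbs much of the difference between settings. Most participants share one setting. Matching load to ability may bring counts at different loads closer together. The planned model also has age, gender, BMI, activity and quality of life, which may carry some of the information behind the choice of setting; the simulation has none of these and may overstate the loss. Extra terms are not free either: with 90% on one setting and r = 0.9, adding them made the standard error about 1% larger. The coefficient is also defined, as the mean difference in repetitions on each person's assigned test.

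All of that stands. It makes the precision loss small. It does not make 30-second and 60-second counts commensurable, and it does not tell a reader what mix of tests lies behind the reported difference.

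Three stronger readings are tempting, and the documents do not support them.

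- *The treatment comparison is biased.* The setting is chosen at the first session, and the Blinding section states that outcome assessors did not know the group. Simulated type I error stayed near 5%.
- *The outcome has no power to spare.* Power is stated only for protein intake. Nothing in the plan says what power leg extensions had or needed.
- *A log-count analysis would recover substantial power.* Simulations that generate a percentage gain with a constant coefficient of variation favour such an analysis by construction, and the plan does not say that effects are proportional. It would also change the estimand to a percentage change.

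**Conclusion.** The omission is plain from the text: up to six settings, one outcome, and no setting term. The consequence is limited to a coefficient whose size depends on the mix of settings, plus a possible small loss of precision. Under the assumed inputs the planned standard error is about 0 to 8% larger than with setting indicators. The loss is under 1% at a baseline correlation of 0.9 and at most 2% when 90% share one setting. The true share and correlation are not given, so the position within that range is unknown. This is a minor point on one of several secondary outcomes and leaves the primary outcomes untouched.

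**What to change.** In the leg-extension models at T2 and T3, add the load-by-duration setting assigned at baseline as a categorical covariate, merging rare settings. Report the number of participants at each setting by arm. Add a sensitivity analysis restricted to those tested with 2.5 kg for one minute. The covariate addresses precision; the restricted analysis gives an effect in a single unit.

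The cost is at most five degrees of freedom, fewer after merging, and a smaller sample in the restricted analysis. No new measurements should be needed, since holding the setting constant across visits implies that it was recorded, although the plan does not say so. A log-count or per-minute analysis is optional. Per-minute scaling leaves the load differences in place, so the setting term would still be needed.
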